4.1 Primary Endpoint

- The primary efficacy parameter is TST time as assessed by a Sleep and Nap Diary after the 13-week, double-blind treatment period.

4.2 Secondary Endpoints

- Sleep latency as assessed by a Sleep and Nap Diary after 13 weeks (Week 15) of double-blind treatment
- Duration of wake after sleep onset period from the Sleep and Nap Diary after 13 weeks (Week 15) of double-blind treatment
- Number of awakenings from the Sleep and Nap Diary after 13 weeks (Week 15) of double-blind treatment
- Longest sleep period from the Sleep and Nap Diary after 13 weeks (Week 15) of double-blind treatment
- Total time in bed from the Sleep and Nap Diary after 13 weeks (Week 15) of double-blind treatment
- Sleep disturbance as assessed by CSDI after 13 weeks (Week 15) of double-blind treatment
- Social functioning at home, in school, and in community settings as assessed by the CGAS after 13 weeks (Week 15) of double-blind treatment
- Behavior at home and in school as assessed by the SDQ after 13 weeks (Week 15) of double-blind treatment
- Number of dropouts during the 13-week (Week 15) double-blind treatment period
- TST time as assessed by actigraphy after the 13-week, double-blind treatment period.
- Sleep latency as assessed by actigraphy after 13 weeks (Week 15) of double-blind treatment

- Duration of wake after sleep onset period as assessed by actigraphy after 13 weeks (Week 15) of double-blind treatment
- Number of awakenings as assessed by actigraphy after 13 weeks (Week 15) of double-blind treatment
- Longest sleep period as assessed by actigraphy after 13 weeks (Week 15) of double-blind treatment
- Sleep efficiency as assessed by actigraphy after 13 weeks (Week 15) of double-blind treatment
- Assessment of AEs throughout the study and upon study withdrawal using the TESS
- Vital signs at each visit including the placebo run-out (withdrawal) period
- Physical examination at each visit including the placebo run-out (withdrawal) period

4.3 Exploratory Endpoints

- Sleep variables as assessed by the Sleep and Nap Diary at baseline (Week 2), after 3 weeks of double blind treatment (Week 5), and after 13, 26, and 39 weeks of open-label treatment (Weeks 28, 41, and 54)
- Sleep disturbance as assessed by the CSDI score at baseline after 3 weeks of double-blind treatment (Week 5), after 13, 26, 39, and 91 weeks of open-label treatment (Weeks 28, 41, 54, and 106, respectively), and at the end of study visit (Week 108)
- Social functioning at home, in school, and in community settings as assessed by the CGAS after 13 weeks (Week 28) of open-label treatment
- Behavior at home and in school as assessed by the SDQ after 13 weeks (Week 28) of open-label treatment
- Caregiver's daytime sleepiness (i.e., NOT the child's) during the study as assessed by the ESS (Weeks 0, 2, 5, 15, 28, 41, 54, 106 and 108)
- Caregiver's well-being (i.e., NOT the child's) during the study as assessed by the WHO-5 questionnaire (Weeks 0, 2, 5, 15, 28, 41, 54, 106 and 108)
- Caregiver's quality of sleep at night (i.e., NOT the child's) during the study using the PSQI global score and components (at Weeks 0, 2, 5, 15, 28, 41, 54, 106 and 108)
- Dosage received by visit and maximum dosage received overall
- BMI and Z-score assessed during the study
- Pubertal assessment using the Tanner scale during the study. The Tanner scale will be used to assess and stage physical development in children ≥ 8 years of age. For children ≤ 5 years of age, only height and head circumference will be used to stage children development. Between the age of 5 and 8, the children's physical development will be determined using BMI.
- In children diagnosed with epilepsy, the number and severity of epilepsy seizures assessed during the study using seizures diaries completed by the parents at the time of the seizures

5 Study Design

This is a randomized placebo-controlled study in children diagnosed with Autism Spectrum Disorders and neurodevelopmental disabilities caused by neurogenetic diseases. Children will have a documented history of these disorders, as confirmed or consistent with the International Classification of Diseases (ICD-10) or Diagnostic and Statistical Manual of Mental Disorders, Fifth Edition, Text Revision (DSM-5/4) criteria, having International Classification of Sleep Disorders (ICSD) criteria-based sleep disturbances modified to take into account the uniqueness of insomnia in the pediatric population at screening.

The children will undergo 4 weeks of basic sleep hygiene and behavioral intervention, which will serve as a wash-out period from any hypnotics; a gradual withdrawal will take place during the first 2 weeks and a complete withdrawal of prohibited medications will take place during the last 2 weeks.

Children who are still found to be eligible for the study after the 4-week, basic sleep hygiene and behavioral intervention wash-out period, will continue in a 2-week single blind (SB) placebo run-in period. In order to be eligible for the 2-week SB placebo run-in period, the child should not have responded to sleep hygiene and behavioral intervention during the first 4 weeks and therefore will not need to continue this therapy during the study. Children with a documented history of sleep hygiene and behavioral intervention, who are still found eligible, will enter directly into the 2-week SB placebo run-in period.

Children with a documented history of sleep hygiene and behavioral intervention who are taking prohibited medications will not require additional training and will undergo a 2-week wash-out period before Visit 1 (e.g., Weeks -2 through 0 to wash out melatonin or any other prohibited medications). During these 2 weeks there is no need to complete the sleep and nap diary.

After the 4-week sleep hygiene (for children who do not have a documented history of sleep hygiene and behavioral intervention) and 2-week SB placebo run-in period, children who are still found eligible for study participation will be randomized in a 1:1 ratio to receive either Circadin® 2 mg or placebo for 3 weeks in a double-blind treatment period. After 3 weeks of treatment, on the last day of Week 5 \pm 3 days (Visit 3), sleep variables will be assessed to determine if dose modification (an increase to 5 mg) is required. Children will then continue on 2 or 5 mg of Circadin® or placebo for an additional double-blind period of 10 weeks. This double-blind period will be followed by an open-label period of 13 weeks. At the end of the 13-week open-label period on the last day of Week 28 \pm 3 days (Visit 5), sleep variables will be assessed to determine if a potential additional dose modification (i.e., an increase either to 5 mg for subjects who are still on 2 mg or an increase to 10 mg for subjects who are on 5 mg) is necessary. Children will continue at 2, 5, or 10 mg Circadin® in an open-label period for another 78 weeks of follow-up, which will include continuous safety monitoring and two efficacy assessment time points at Weeks 41 and 54. The study will end with a 2-week SB placebo run-out period.

6 Statistical Considerations

6.1 Sample Size

To achieve 95% power at the 5% level for the primary objective (assuming a change of 0.72 hour in the Circadin® arm and 0.27 hour in the placebo arm and a standard deviation (SD) of 0.69 in the Circadin® arm and 0.45 in the placebo arm), 45 subjects are required per combined group. Therefore, 90 subjects in total are required to complete Visit 5. These estimations are based on previous studies conducted with Circadin®.

6.2 Randomization

At Visit 1, enough eligible male and female children, of ages 2 to 17.5 years, will be screened for the study to allow for 120 subjects to then be randomized in a 1:1 ratio to receive Circadin® or placebo at Visit 2. A minimum of 90 children are expected to complete the double-blind and first open-label period (up to Week 28). A minimum of 50 children are expected to complete the second open-label safety follow-up period.

7 Protocol Deviations

Major protocol deviations are defined as those deviations from the study protocol that may have the ability to impact the efficacy results. As such, subjects with major deviations occurring up to the end of the double-blind phase will be excluded from the per-protocol (PP) population (as defined in Section 8.5).

Major protocol deviations include (but are not limited to):

- Deviation from inclusion/exclusion criteria
- Withdrawal criteria met during the study but subject was not withdrawn
- Prohibited concomitant medications
- Substantial deviations from the dosing schedule (Subjects received at least 5 of 7 doses in the week prior to the scheduled visit and treatment compliance is within the range >60%)
- Substantial deviations in the completion of the sleep and nap diary (Subjects must have completed the diary at least 3 out of 7 nights per week over the two weeks prior to the scheduled visit and have a valid mean TST value at Visit 4)

Where possible, major deviations will be programmatically verified by Datatrial. Listings of concomitant medications in Excel format will be provided to the sponsor by Datatrial for review to identify prohibited medications prior to unblinding.

Major protocol deviations occurring up to the end of the first open-label phase will be identified during a Blinded Data Review Meeting (BDRM) prior to database lock and unblinding.

The purpose of the BDRM will be two-fold; It will be used to review and confirm the data identified as protocol deviations as detailed above. It will also be used to review the Sleep and Nap diary and confirm that the data is correct and/or identify implausible values and document any changes that are made to the source data. Blinded SAS listings of the Sleep and Nap diary data including derivation of mean TST will be provided by

Datatrial in advance of the BDRM to aid this review. Any changes to the source data may require a further review of the protocol deviations.

8 Analysis Populations

8.1 All Enrolled Set

The All Enrolled Set will include all subjects who have given written informed consent. This set will be used for subject disposition and demographic characteristic summaries, and disposition, eligibility and demographic listings.

8.2 All Randomized Set

The All Randomized Set will include the subjects from the All Enrolled Subset who have been randomized. Subjects will be classified according to randomized treatment. This set will be used for demographic characteristic, and baseline characteristic summaries, and all listings excluding disposition, eligibility and demographic listings.

Furthermore, the All Randomized Set will be used for the sensitivity analyses of missing efficacy data as detailed in Section 11.4.

8.3 Safety Set

Safety analyses will be performed on the Safety Analysis Set, which includes all subjects randomized to treatment who take at least one dose of study medication. Subjects will be classified according to actual treatment received. This analysis set will be used for all safety analyses.

8.4 Full Analysis Set

Efficacy analyses will be performed on the Full Analysis Subset (FAS), and will include all subjects in the Safety Analysis Set who satisfy all major entry criteria (Inclusion Criteria 1-5) and who have a valid mean TST result recorded for baseline and at least one post-baseline period assessment during the double blind phase. Subjects will be classified according to randomized treatment. This analysis set will be used for all efficacy analyses.

8.5 Per Protocol Set

The Per Protocol (PP) Set is a subset of the FAS, which excludes all subjects for whom there were major violations of the protocol as detailed in Section 7. Subjects will be classified according to randomized treatment. This analysis subset will be used for sensitivity analyses of the primary endpoint and select secondary endpoints.

9 Data Reporting Conventions

9.1 Descriptive Statistics

Unless otherwise stated, all continuous parameters will be summarized using standard summary statistics as appropriate (n, mean, standard deviation, minimum, median and maximum). In presentations of summary statistics, the minimum and maximum will be displayed to the same number of decimal places as the variable being summarized was recorded to. The mean and median will be displayed to one extra decimal place; the standard deviation (SD) will be displayed to two extra decimal places.

Categorical variables (e.g., gender) will be summarized using frequency counts and percentages. Unless otherwise stated, these presentations will consist of the number of subjects in a particular category and the percentage of the total number of subjects. Percentages will be presented to one decimal place.

Unless otherwise noted, all analyses will be conducted using the validated statistical software Statistical Analysis System (SAS) version 9.3.

9.2 Reporting of Phases

Unless otherwise specified, tables will be reported separately for the Double Blind and Open Label phases. Tables reporting the Double Blind phase will be presented by treatment group.

In addition, baseline demographic and history tables will include an Overall column.

Tables reporting data from the Open Label phases will be presented by the original Double Blind treatment group and will also include an 'All Circadin' group. Unless otherwise specified, the two Open Label phases will be reported in the same table. For the main analysis, the Open Label tables will only include data for Visit 5. On completion of the study, the open label tables will be re-run to include all data up to the end of the study.

9.3 Baseline Derivation

For all efficacy and safety variables, the baseline value will be calculated as the last recorded value prior to the start of randomized treatment.

9.4 Missing Dates

For partial date of births, where the day and month are missing, they will be replaced with 30/06.

The following will be applied to start and end dates for baseline histories, concomitant medications and adverse events where required for calculation of durations and assignment to phases. No imputed values will appear in the listings.

- If the day is unknown and the month and the year are known, it will be replaced by 01 in the case of a start date or by the last day of the month in the case of an end date.

- If the day and the month are unknown, they will be replaced by 01/01 in the case of a start date or 31/12 in the case of an end date.
- If the day, the month and the year are unknown, the date will be considered as missing.

For start and end dates of AEs, there is an exception from the above mentioned rules:

- If the day is unknown and the month and the year are the same as the first treatment intake known, it will be replaced by the date of first treatment intake.
- If the day and the month are unknown and the year is the same as the first treatment intake known, it will be replaced by the date of first treatment intake.

10 Subject Disposition, and Demographic and Baseline Characteristics

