12.11 HANDLING OF DROPOUTS/MISSING DATA

Missing data will not be replaced for both primary and secondary criteria. The following will be applied concerning start and end dates:

- If the day is unknown and the month and the year are known, it will be replaced by 01 in case of a start date or by the last day of the month in case of an end date.
- If the day and the month are unknown, they will be replaced by 01/01 in case of a start date or 31/12 in case of an end date.
- If the day, the month and the year are unknown, the date will be considered as missing.

For start and end dates of AEs, there is an exception from the above mentioned rules:

- If the day is unknown and the month and the year are the same as the first treatment intake known, it will be replaced by the date of first treatment intake.
- If the day and the month are unknown and the year is the same as the first treatment intake known, it will be replaced by the date of first treatment intake.

At least 3 documented attempts must be made to contact any patient lost to follow-up at any 1 time point prior to the last scheduled contact (clinic visit or telephone contact). One of these documented attempts must include a written communication sent to the patient's last known address via a courier or mail (with acknowledgement of receipt request) asking that they return any unused IMP and return to the clinic/site for final safety evaluations.

Sleep and Nap Diaries should not be amended by site personnel, with exception of the following situations:

- Dates presented with inconsistent formatting can be edited for consistency.
- Missing or incorrect dates in a sequence can be corrected (e.g., the dates Dec 2014 to Jan 2014 could be corrected to Dec 2014 to Jan 2015)
- Time entered using the 12-hour format can be revised to the 24-hour format.
- Hours can be converted to minutes and vice versa, as needed.

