10.6 Prior and Concomitant Medications

Concomitant medications recorded during the study will be coded using World Health Organization (WHO)-Drug. Details of concomitant medication will be listed.

Concomitant medications will be summarized according to whether they were being taken pre-study (prior medications) and/or during the study (concomitant medication). Prior medications are any that were being taken prior to the first dose of study medication (medication stop date prior to the first dose of study medication). Concomitant medications are any that were being taken on or after the first dose of study medication. If the start and stop dates of the concomitant medications do not clearly define the period during which a medication was taken, it will be assumed to be a concomitant medication.

Concomitant medications will be assigned to the phase they were taken: Double-Blind, first Open-Label, second Open-Label. If a concomitant medication starts or is ongoing between Visit 2 and Visit 4, it will be assigned to the Double-Blind phase. If a concomitant medication starts or is ongoing between Visit 4 + 1 day and Visit 5, it will be assigned to the first Open-Label phase. If a concomitant medication starts or is ongoing between Visit 5 + 1 day and Visit 8, it will be assigned to the second Open-Label phase. If the start and stop dates of the concomitant medications do not clearly define the phase during which a medication was taken, it will be assumed to be taken across all phases.

Prior and concomitant medications will be summarized by Anatomical Therapeutic Chemical (ATC) level 2 term and preferred term.

Details of non-pharmacological concomitant measures will be listed.

11 Efficacy

Subjects will be classified and summarized by randomized treatment. For all efficacy assessments, the baseline values will be calculated as the last recorded value prior to the start of randomized treatment. Change from baseline values will be calculated as the assessment score minus the baseline value. For questionnaires the change from baseline values will be calculated for each item and total/subscale score as applicable.

All summaries and analyses will be performed on the FAS set. The primary efficacy endpoint and select secondary efficacy endpoints will also be analyzed on the PP set. Analyses looking at the impact missing data on the primary efficacy endpoint will also be performed on the All Randomized set.

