12.3 Adverse Events

AEs will be coded according to MedDRA® version 18.0 or higher.

An overall AE summary will be presented for the following pre-defined subsets of events:

- Any TEAEs
- Any TEAEs considered related to treatment
- Any TEAEs leading to study drug discontinuation
- Any SAEs
- Any deaths
- Any SAEs considered related to treatment
- Any SAEs leading to study drug discontinuation

Listings by subject will be presented for the following subsets:

- Any TEAEs

- Any SAEs

All TEAEs will be summarized and grouped by MedDRA® System Organ Class (SOC) and specific AE preferred term (PT). Results will be displayed in order of decreasing frequency by SOC and PT.

Summaries will also be produced of SAEs, treatment related AEs and TEAEs leading to study drug discontinuation by SOC and PT terms. In addition, a summary will be provided by severity (mild, moderate, severe).

For all summary tables, both number of events and number of subjects will be tabulated. For subjects, percentages will be calculated from the total number of subjects per treatment group. Related to treatment is defined as any adverse events considered either “possibly”, “probably” or “definitely” related to study drug.

Tables will be presented for the double blind and open-label phases separately.

In addition a cumulative summary will also be presented for all subjects on active treatment for all TEAEs, SAEs and TESAEs leading to discontinuation of study drug grouped by SOC and PT terms occurring in either the double blind or open-label phase.

For the purposes of the interim analysis reporting, an AE cut-off point will be defined as any AE starting on or before Visit 5.

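### An adverse event with an unknown start day in the Visit 4 month is always dated on or before Visit 4, so open-label Circadin events in placebo-randomised children can be counted as double-blind placebo events

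*SAP*

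**What the plan says.** SAP 9.4 applies its date rules to baseline histories, concomitant medications and "adverse events where required for calculation of durations and assignment to phases". When only the day of a start date is missing, "it will be replaced by 01 in the case of a start date".

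One exception follows for AEs: "For start and end dates of AEs, there is an exception from the above mentioned rules". Its first bullet begins "If the day is unknown and the month and the year are the same as the first treatment intake known", and its second covers a date with only the year known, when that year is the year of first intake. Both substitute the date of first treatment intake. Protocol 12.11 has the same rules and the same substitution ("it will be replaced by the date of first treatment intake"). Neither document says whether first treatment intake means the run-in placebo dispensed at Visit 1 or the first randomised dose.

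For reporting, SAP 12.3 says "Tables will be presented for the double blind and open-label phases separately". SAP 9.2 shows double-blind tables by treatment group and open-label tables by original group plus an 'All Circadin' group. SAP 12.3 adds a cumulative summary of events on active treatment. After Visit 4 every continuing child receives open-label Circadin (Protocol 7).

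The line between the phases is written only for concomitant medications, in SAP 10.6: "If a concomitant medication starts or is ongoing between Visit 2 and Visit 4, it will be assigned to the Double-Blind phase", with the first open-label phase starting the day after Visit 4. For AEs, the only boundary in SAP 12.3 is the Week 28 cut-off: "an AE cut-off point will be defined as any AE starting on or before Visit 5".

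**The concern.** The exception stops an AE in the month treatment began from being dated before treatment. A child randomised to placebo has a second start of treatment, the first open-label Circadin dose after Visit 4, and no rule protects that month. An event that began on Circadin can be dated back into the placebo period.

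Two outputs are at stake. The double-blind placebo column can gain events that arose on active drug. The 'All Circadin' open-label group and the cumulative active-treatment summaries can lose those same events. Both belong to the Week 28 report that is submitted for approval.

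The exception has two smaller faults of its own: it covers end dates as well as start dates, and its anchor date is undefined.

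**Working it through.** The plan states no figure to reproduce. The check is one of date logic.

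**Inputs.** Unknown start day becomes day 1 (SAP 9.4). Visit 2 is the last day of Week 2 and Visit 4 the last day of Week 15, each ±3 days (Protocol Table 5-1). Phase boundary: on or before Visit 4 is double-blind (SAP 10.6, borrowed for AEs).

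**1. Can the first-intake exception apply in the Visit 4 month?** Visit 2 to Visit 4 is 13 × 7 = 91 days. With both windows used against each other it is 91 − 6 = 85 days, longer than any month. Stepping Visit 4 through 1,461 consecutive calendar dates with the 91-day gap gave 0 dates on which the two visits shared a month. If first intake means the run-in dose, the gap is longer still.

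**2. Where do the events go?** Day 1 of the Visit 4 month is never later than Visit 4, so 100% of unknown-day AEs in that month are filed as double-blind. That includes 100% of those that began after Visit 4.

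**3. What share of these is misfiled?** In a 30-day month with Visit 4 on day d and onset uniform over the month (assumption), the share is (30 − d)/30:

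| Visit 4 on day | Share truly open-label |
|---|---|
| 1 | 29/30 = 97% |
| 10 | 20/30 = 67% |
| 15 | 15/30 = 50% |
| 30 | 0/30 = 0% |

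Averaged over the 1,461 dates and actual month lengths, the share is 48%.

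**4. How many events?** The documents give no rate of partial AE dates. For scale only, let p be the share of AEs with no start day and let onset be uniform over the 91-day first open-label phase. About 15 days of the Visit 4 month remain on average, so the share of ex-placebo open-label AEs that moves is p × 15/91 = p × 16.5%. At p = 10% this is 1.6%; at p = 30% it is 4.9%. Nothing in the documents supports either value of p.

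**5. What happens to the treatment comparison?** Let C and P be the true double-blind AE counts in the Circadin and placebo columns, and let b and a be the open-label events pulled into each. The reported difference is (C + b) − (P + a) = (C − P) + (b − a). It is unchanged if a = b and understated only if a > b.

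**6. End dates.** Suppose first intake is on the 10th and an AE starts on the 20th, with its end day unknown in the same month. The exception sets the end to the 10th, before onset.

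**7. Meaning of first intake.** If it is the run-in dose, an unknown-day AE in the Visit 2 month is dated either to that dose or to the 1st. Either falls on or before Visit 2, so true double-blind events are pulled back towards the run-in.

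**The case against.** The strongest objection concerns the comparison between arms. A reader might infer that inflating the placebo column understates the Circadin-placebo difference in AEs. The documents do not support that. The same rule pulls post-Visit 4 events into the Circadin double-blind column, and after Visit 4 both arms take Circadin. With similar AE and partial-date rates, a and b are about equal: the absolute difference is unchanged in expectation, and at most the ratio is diluted. Understatement needs the further premise that new users have more AEs just after Visit 4 than continuing users. This objection stands.

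The AE phase boundary is also inferred, from a rule for medications and from a cut-off based on start dates. That stands as a condition on the point. If the wording for medications that start or are ongoing were carried over to AEs, an event could appear in the open-label table as well, but it would still enter the placebo double-blind column.

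The size is probably small. AEs and the TESS questionnaire are recorded at every visit from Visit 2, families are phoned weekly up to Visit 7, and eCRF entries are checked and queried. The end-before-start fault reaches no planned table, since no AE duration summary is listed and SAP 9.4 keeps imputed dates out of the listings.

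Finally, dating every such event to the first open-label dose would be no better: about 52% of them (100 − 48) began on or before Visit 4 and would be misfiled the other way. That stands against a blanket rule. It does not stand against using the reporting visit and end date, which bound the onset.

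**Conclusion.** The point holds as a minor fault in a stated rule. If AE phase follows the imputed start date, every unknown-day AE in the Visit 4 month is filed as double-blind, and about 48% of those wrongly so under uniform timing. For placebo-randomised children this charges Circadin-onset events to placebo and can remove them from the active-treatment tables. For the Circadin arm the drug is right and only the phase is wrong.

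The number of events is unknown and probably small. An understated absolute Circadin-placebo difference is not established. The end-date fault and the undefined first intake are genuine but of little consequence for the planned outputs.

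**What to change.** Amend SAP 9.4, and record the change in SAP section 14 because Protocol 12.11 has the same rule.

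1. For an AE with an unknown start day in the Visit 4 month, assign the phase from the visit at which it was first reported and from its end date. An AE recorded at or before Visit 4, or ending on or before it, is double-blind. One first reported after Visit 4 is dated to the first open-label dose. Where the order is still unresolved in a placebo-randomised child, use the first open-label dose. State the AE phase boundary that this relies on.
2. State that first treatment intake means the first randomised dose.
3. Limit the first-intake exception to start dates, and impute an unknown end day as the last day of the month, so that no end date precedes its start.

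The cost is a few sentences and slightly more programming. No new data are needed and no efficacy analysis changes. The downside is that a few true placebo-phase events may be attributed to Circadin. In the Circadin arm, a double-blind event first reported after Visit 4 would likewise be filed as open-label; recording AEs at Visit 4 itself limits both.
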